City of Hope Comprehensive Cancer Center
Rationale for this Study:

At present, 3rd line therapy of mRCC remains an area of need. Pazopanib has shown activity in the setting of bevacizumab- and cytokine- refractory patients.^{1,2} Furthermore, there may be preclinical rationale to challenge patients with a structurally distinct VEGF-TKI. Molecular aberrations in the receptor tyrosine kinase (RTK) targeted by VEGF-TKIs may confer a relative resistance to specific agents – thus, re-challenging with agents such as sunitinib is presumably less efficacious.^{3,4} Ongoing studies have assessed inhibition of distinct molecular pathways; however, response rates using this approach (i.e., with mTOR inhibitors or perifosine) have been modest at best.^{5,6} 3rd- line therapy represents an area of need in metastatic renal cell carcinoma – herein, we propose use of pazopanib in this setting.

Primary Objective:
To determine the RR associated with pazopanib as 3rd-line therapy in mRCC patients who have failed therapy with a distinct VEGF-TKI
Secondary Objective(s):

• To evaluate progression-free survival (PFS), overall survival (OS)• To describe the toxicity associated with pazopanib in this patient population• To compare, within patient, time to tumor progression of 2nd-line therapy with time to tumor progression on pazopanib as 3rd-line therapy• To determine if baseline HGF, E-selectin and IL-6 are associated with PFS• To determine if pre-metastatic niche density in regional LNs is associated with PFS• To determine an association between E-selectin, IL-6 and pre-metastatic niche density• To evaluate the prognostic effect of pre-metastatic niches as an independent factor in PFS• To determine if pSTAT3 in tumor tissue is associated with PFS
Study Design:
Open-label, single institution phase II study
Primary Endpoint and Secondary Endpoints:
Primary:

- RR by RECIST 1.1 Criteria

Secondary:

- Toxicity, PFS, OS

Sample Size:

28

Estimated Duration of the Study

12 months

Summary of Subject Eligibility Criteria:

Inclusion Criteria:

- Histologically confirmed diagnosis of metastatic clear cell RCC
- At least one measurable lesion at baseline as per RECIST 1.1 criteria. If skin lesions are reported as target lesions, they must be documented (at baseline and at every physical exam) using color photography and a measuring device (such as a caliper) in clear focus to allow the size of the lesion to be determined from the photograph
- 1 prior VEGF-TKI required
- 1 other prior systemic therapy allowed
- ECOG PS 0-1
- Resolution of grade ≥ 2 toxicity from prior therapy
- Normal hematologic labs and serum chemistries (to be specified in the protocol)
- Subjects must provide written informed consent prior to performance of study-specific procedures or assessments, and must be willing to comply with treatment and follow-up. Procedures conducted as part of the subject's routine clinical management (e.g., blood count, imaging study) and obtained prior to signing of informed consent may be utilized for screening or baseline purposes provided these procedures are conducted as specified in the protocol.
- Age ≥ 18 years or legal age of consent if greater than 18 years
- A female is eligible to enter and participate in this study if she is of non-child bearing potential (i.e., physiologically incapable of becoming pregnant), including any female who has had (1) a hysterectomy, (2) a bilateral oophorectomy (ovariectomy), (3) a bilateral tubal ligation, or (4) is post-menopausal. Subjects not using hormone replacement therapy (HRT) must have experienced total cessation of menses for ≥ 1 year and be greater than 45 years in age, OR, in questionable cases, have a follicle stimulating hormone (FSH) value >40 mIU/mL and an estradiol value < 40 pg/mL (<140 pmol/L). Subjects using HRT must have experienced total cessation of menses for ≥ 1 year and be greater than 45 years of age OR have had documented evidence of menopause based on FSH and estradiol concentrations prior to initiation of HRT.
- Patients with childbearing potential, including any female who has had a negative serum pregnancy test within 2 weeks prior to the first dose of study treatment, preferably as close to the first dose as possible, and agrees to use adequate contraception. GSK acceptable contraceptive methods, when used consistently and in accordance with both the product label and the instructions of the physician, are as follows: (1) complete abstinence from sexual intercourse for 14 days before exposure to investigational product, through the dosing period, and for at least 21 days after the last dose of

investigational product, (2) oral contraceptive, either combined or progestogen alone, (3) injectable progestogen, implants of levonorgestrel, estrogenic vaginal ring, percutaneous contraceptive patches, intrauterine device (IUD) or intrauterine system (IUS) with a documented failure rate of less than 1% per year, (4) male partner sterilization (vasectomy with documentation of azoospermia) prior to the female subject's entry into the study, and this male is the sole partner for that subject, (6) double barrier method: condom and an occlusive cap (diaphragm or cervical/vault caps) with a vaginal spermicidal agent (foam/gel/film/cream/suppository) Female subjects who are lactating should discontinue nursing prior to the first dose of study drug and should refrain from nursing throughout the treatment period and for 14 days following the last dose of study drug.

- Adequate organ system function as defined in Table 1

Exclusion Criteria:

- Concurrent use of other investigational agents
- Known history of allergic reactions to pazopanib or other VEGF-TKIs
- Presence of serious or uncontrolled infection
- Prior malignancy. (Note: Subjects who have had another malignancy and have been disease-free for 3 years, or subjects with a history of completely resected non-melanomatous skin carcinoma or successfully treated in situ carcinoma are eligible.
- History or clinical evidence of central nervous system (CNS) metastases or leptomeningeal carcinomatosis, except for individuals who have previously-treated CNS metastases, are asymptomatic, and have had no requirement for steroids or anti-seizure medication for 6 months prior to first dose of study drug. Screening with CNS imaging studies (computed tomography [CT] or magnetic resonance imaging [MRI]) is required only if clinically indicated or if the subject has a history of CNS metastases.
- Clinically significant gastrointestinal abnormalities that may increase the risk for gastrointestinal bleeding including, but not limited to (1) active peptic ulcer disease, (2) known intraluminal metastatic lesion/s with risk of bleeding, (3) inflammatory bowel disease (e.g. ulcerative colitis, Crohn's disease), (4) other gastrointestinal conditions with increased risk of perforation, or (5) history of abdominal fistula, gastrointestinal perforation, or intra-abdominal abscess within 28 days prior to beginning study treatment.
- Clinically significant gastrointestinal abnormalities that may affect absorption of investigational product including, but not limited to (1) malabsorption syndrome or (2) major resection of the stomach or small bowel.
- Presence of uncontrolled infection.
- Corrected QT interval (QTc) > 480 msec using Bazett's formula
- History of any one or more of the following cardiovascular conditions within the past 6 months: (1) cardiac angioplasty or stenting, (2) myocardial infarction, (3) unstable angina, (4) coronary artery bypass graft surgery, (5) symptomatic peripheral vascular disease, or (6) Class III or IV congestive heart failure, as defined by the New York Heart Association (NYHA)
- Poorly controlled hypertension [defined as systolic blood pressure (SBP) of ≥ 140 mmHg or diastolic blood pressure (DBP) of ≥ 90 mmHg]. (Note: Note: Initiation or adjustment of antihypertensive medication(s) is permitted prior to study entry. BP must be re-assessed

on two occasions that are separated by a minimum of 1 hour; on each of these occasions, the mean (of 3 readings) SBP / DBP values from each BP assessment must be <140/90 mmHg in order for a subject to be eligible for the study.

- History of cerebrovascular accident including transient ischemic attack (TIA), pulmonary embolism or untreated deep venous thrombosis (DVT) within the past 6 months. (Note: Subjects with recent DVT who have been treated with therapeutic anti-coagulating agents for at least 6 weeks are eligible)
- Prior major surgery or trauma within 28 days prior to first dose of study drug and/or presence of any non-healing wound, fracture, or ulcer (procedures such as catheter placement not considered to be major).
- Evidence of active bleeding or bleeding diathesis.
- Known endobronchial lesions and/or lesions infiltrating major pulmonary vessels
- Hemoptysis in excess of 2.5 mL (or one half teaspoon) within 8 weeks of first dose of study drug.
- Any serious and/or unstable pre-existing medical, psychiatric, or other condition that could interfere with subject's safety, provision of informed consent, or compliance to study procedures.
- Unable or unwilling to discontinue use of prohibited medications list as specified in the full protocol for at least 14 days or five half-lives of a drug (whichever is longer) prior to the first dose of study drug and for the duration of the study.
- Treatment with any of the following anti-cancer therapies: (1) radiation therapy, surgery or tumor embolization within 14 days prior to the first dose of pazopanib OR (2) chemotherapy, immunotherapy, biologic therapy, investigational therapy or hormonal therapy within 14 days or five half-lives of a drug (whichever is longer) prior to the first dose of pazopanib
- Any ongoing toxicity from prior anti-cancer therapy that is >Grade 1 and/or that is progressing in severity, except alopecia.
- Medications that inhibit CYP3A4 may result in increased plasma pazopanib concentrations; therefore, co-administration of strong CYP3A4 inhibitors is PROHIBITED beginning 14 days prior to the first dose of study drug until discontinuation from the study. Strong CYP3A4 inhibitors include (but are not limited to): certain antibiotics (including clarithromycin, telithromycin, and troleandomycin), certain HIV protease inhibitors (including ritonavir, indinavir, saquinavir, nelfinavir, amprenavir, and lopinavir), certain ntifungals (including itraconazole, ketoconazole, voriconazole, and fluconazole) and certain antidepressants (including nefazodone).

Investigational Product Dosage and Administration:

Pazopanib 200 mg 4 tablets oral daily

Clinical Observations and Tests to be Performed:

Assessments within 28 Days of the First Dose

- RCC-specific history including: date of diagnosis, primary tumor type with histology/cytology determination, current stage of cancer, prior systemic treatment(s) for RCC, ongoing toxicity related to prior treatment(s); and history of other malignancies
- Prior surgery and/or radiotherapy (date, organ/anatomic region(s) of surgery and/or radiotherapy must be documented), other significant medical and surgical histories within the past 6 months.
- Baseline bone scan for tumor assessment
- Baseline disease assessments with CT of the chest, abdomen or pelvis
- MRI or CT of the brain within 2 weeks of first dose if clinically indicated or if the subject has a history of CNS metastases

Assessments within 7 Days of the First Dose

- Physical examinations: height (only recorded at baseline) and body weight and current medical conditions.
- Vital signs: body temperature, blood pressure and heart rate. **Note:** If a subject presents with poorly controlled hypertension, defined as SBP \geq 140mmHg or DBP \geq 90mmHg, antihypertensive medication(s) should be initiated or adjusted with a goal to control the blood pressure to $<$ 140/90 mmHg.
- ECOG PS
- Clinical laboratory assessments, listed in 6.2
- 12-lead ECG with QTc measurement
- Baseline IL-6 and E-selectin assessment
- Serum pregnancy test for women of childbearing potential.

Pre-dose Assessments on Day 1

- Physical examination: to identify any changes in the subject's mental and medical conditions since baseline assessment that would make him/her ineligible for the study.
- Blood pressure measurements: subjects must have a blood pressure reading of $<$ 140/90mmHg to be eligible. If anti-hypertensives were initiated and/or dosing has been adjusted during the Baseline Period, the blood pressure must be re-assessed on two occasions consecutively that are separated by a minimum of 1 hour. The mean SBP/DBP values from both blood pressure assessments must be $<$ 140/90mmHg in order for a subject to be eligible. These two assessments must also be the most recent ones prior to randomization (the blood pressure values from the later assessment will be used as the subject's baseline blood pressure values). All the blood pressure readings must be recorded on the appropriate eCRF.
- ECOG PS: Any changes since baseline assessment should be recorded in the eCRF. Subjects having deterioration of ECOG PS to $>$ 1 will be excluded from the study.
- Record all the medication(s) received within 2 weeks prior to the first dose of study medication and indicate if the medication is continuing.
- Obtain archived tumor tissue samples for biomarker assessments (if available).

Assessments on Study

- Physical examination: to identify any changes in the subject's mental and medical conditions since baseline assessment that would make him/her ineligible for the study. This will occur at C1D15, C2D1 and monthly thereafter (1 cycle = 28 days).
- ECOG PS: Any changes since baseline assessment should be recorded in the eCRF. Subjects having deterioration of ECOG PS to ≥ 2 will be excluded from the study. This will occur at C1D15, C2D1 and monthly thereafter (1 cycle = 28 days).
- Obtain blood sample for IL-6 and E-selectin measurement. This will occur monthly while patients are on study.
- Tumor assessments will be performed every 8 weeks (+/- 1 week) from randomization until the start of another anticancer therapy. A partial or complete response warrants confirmation no sooner than 4 weeks and no later than 6 weeks after its initial observation. This confirmatory scan is considered outside of standard of care, and will be funded by the sponsor.

Post-Study Assessments

- Any research participant who is discontinued from study treatment for any reason other than PD will continue to have tumor assessments every 8 weeks (+/- 1 week) until the patient starts another anticancer therapy. The investigator or his/her designee will continue collecting information on the initiation of anticancer therapies until the date of data cutoff for the final analysis. All new anticancer therapy therapies after the last dose of treatment will be recorded on the appropriate CRF.
- All research participants will be followed for survival every 6 months.

Clinical Laboratory Assessments

All clinical laboratory assessments will be performed at City of Hope. Laboratory tests should be performed at baseline, at specified visits during the study, and at the follow-up visit, all as indicated in the Time and Events Table(s). Laboratory assessments may be performed within 3 days before the actual visit to allow flexibility in scheduling. Assessments may be performed more frequently if clinically indicated.

All laboratory tests with values that become clinically abnormal while the subject is participating in the study or within 28 days after the last dose of study drug should be repeated at the PI's discretion until the values return to normal or baseline.

Results for all unscheduled clinical laboratory assessments (i.e., hematology, TSH/T₄, coagulation parameters) should be recorded on an unscheduled laboratory form in the eCRF.

Hematology and Clinical Chemistry

Appendix A shows the hematology and clinical chemistry laboratory parameters that should be reported. Assays for hematology and clinical chemistry should be performed at baseline, every 4 weeks until 6 months, and then every 8 weeks thereafter. Hepatic assays should be performed at

baseline, 2, 4, and 8 weeks, followed by every 4 weeks until 6 months, and then every 8 weeks thereafter.

Liver Function Tests

When a separate liver function test (LFT) panel is conducted, this panel should include the following: ALT, AST, alkaline phosphatase, GGT, and total bilirubin. A direct bilirubin level should be obtained if the total bilirubin level is greater than $1.5 \times$ upper limit of normal (ULN). Liver chemistry threshold stopping criteria and dose modification guidelines have been designed to ensure subject safety.

Evaluation of Proteinuria

Proteinuria will be evaluated using the urine protein to creatinine ratio (UPC; see Appendix C). UPC will be determined at times specified in the Time and Events Table. If $UPC \geq 3$, then the dose modification table guidelines should be followed.

Coagulation Tests

Coagulation tests should be performed as specified in the Time and Events Table and also in response to an AE/SAE as clinically indicated. Coagulation tests include activated partial thromboplastin time (aPTT) and either prothrombin time (PT) or international normalized ratio (INR).

Lipid Tests

Lipid tests include cholesterol, high-density lipoprotein (HDL), low-density lipoprotein (LDL), and triglycerides. These tests should be performed as specified in the Time and Events Table. Additional testing may be performed if clinically indicated. In such a case, the subject should be in a fasting state.

Thyroid Function Tests

Thyroid function tests to assess thyroid stimulating hormone (TSH) and thyroxine (free T₄) should be performed as specified in the Time and Events Table. Unscheduled thyroid function tests (TSH and free T₄) may be performed if clinically indicated (e.g., if a subject develops signs and symptoms suggestive of hypothyroidism).

Statistical Considerations:

The primary endpoint is the confirmed response rate (CR+PR), as determined by the RECIST 1.1

criteria. We will employ the two stage MinMax design suggested by Simon.

Prior data indicates that an overall RR of 20% can be obtained with pazopanib therapy. For patients with mRCC eligible for this 3rd line study, a response rate of 20% would represent a significant improvement over current approaches (3rd line therapy with the Akt inhibitor perifosine, for instance, yielded a 7% response rate) and would further indicate that the activity of pazopanib is maintained through multiple prior lines of therapy in selected patients.

Prior studies suggest that a response rate between 5-10% would not be an improvement over current approaches. As a result, we have set a discouraging response rate at 8%, and an encouraging response rate at 23%. Initially, we will accrue 14 patients. If there is at least 1 responder, accrual will continue to 28 patients. If 5 or more responders (18%) are observed, pazopanib will be declared promising for future studies, assuming toxicity and survival endpoints are also within acceptable limits. This Simon's MiniMax two-stage design has a type I error of 10% (probability of declaring an agent with a true 8% response rate as promising), and a power of 80% (probability of *not* declaring an agent promising with a true 23% response rate is 10%). All eligible patients treated will be included in the calculation of response rate. Any patients with an unknown response rate will be included as a non-responder.

This design has 31% chance of stopping at the first stage if true response rate is 8%.

Toxicity will be monitored on an ongoing basis. If the number of unacceptable toxicities exceeds 1 in the first 3, or exceeds 2 in the first 6 or more than 25% thereafter, the study will hold accrual for an amendment regarding treatment modifications or study termination. Toxicity will be graded and recorded for each patient in this population according to CTCAE 4.0.

Secondary endpoints include progression-free survival (PFS), overall survival (OS), and toxicity, and we will also compare PFS on this study to time to progression on the previous line of therapy.

Additional secondary endpoints relate to biological correlates, including E-Selection, IL-6, the pre-metastatic niche density, pSTAT3, and baseline HGF. Because the nature of these secondary endpoints is exploratory, we will not consider the issue of multiple comparisons and the according adjustment of p-values.

Univariate or multivariate Cox proportional hazards model will be invoked to assess the association of these biological correlates and both PFS and OS.

In addition, a t-test will be conducted to determine if there is an association between E-selectin, IL-6 and the pre-metastatic niche density.

Table of Contents

SECTION	PAGE
1.0 Goals and Objectives (Scientific Aims).....	17

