1.2 Secondary Objectives

- 1.2.1 To determine if baseline HGF, E-selectin and IL-6 are associated with PFS
- 1.2.2 To determine if pre-metastatic niche density in regional LNs is associated with PFS
- 1.2.3 To determine an association between E-selectin, IL-6 and pre-metastatic niche density
- 1.2.4 To evaluate the prognostic effect of pre-metastatic niches as an independent factor in time to first relapse
- 1.2.5 To determine if pSTAT3 in tumor tissue is associated with PFS
- 1.2.6 To describe the toxicity associated with pazopanib in this patient population
- 1.2.7 To evaluate PFS and OS
- 1.2.8 To compare, within patient, time to tumor progression of 2nd-line therapy with time to tumor progression on pazopanib as 3rd-line therapy

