3.0 Patient Eligibility

3.1 Inclusion Criteria

- 3.1.1 Histologically confirmed diagnosis of metastatic clear cell RCC
- 3.1.2 At least one measurable lesion at baseline as per RECIST 1.1 criteria. If skin lesions are reported as target lesions, they must be documented (at baseline and at every physical exam) using color photography and a measuring device (such as a caliper) in clear focus to allow the size of the lesion to be determined from the photograph
- 3.1.3 1 prior VEGF-TKI required
- 3.1.4 1 other prior systemic therapy allowed
- 3.1.5 ECOG PS 0-1
- 3.1.6 Resolution of grade ≥ 2 toxicity from prior therapy
- 3.1.7 Normal hematologic labs and serum chemistries (see table 1, under 3.1.12 for definition of normal)
- 3.1.8 Subjects must provide written informed consent prior to performance of study-specific procedures or assessments, and must be willing to comply with treatment and follow-up. Procedures conducted as part of the subject's routine clinical management (e.g., blood count, imaging study) and obtained prior to signing of informed consent may be utilized for screening or baseline purposes provided these procedures are conducted as specified in the protocol.
- 3.1.9 Age ≥ 18 years or legal age of consent if greater than 18 years
- 3.1.10 A female is eligible to enter and participate in this study if she is of non-child bearing potential (i.e., physiologically incapable of becoming pregnant), including any female who has had (1) a hysterectomy, (2) a bilateral oophorectomy (ovariectomy), (3) a bilateral tubal ligation, or (4) is post-menopausal. Subjects not using hormone replacement therapy (HRT) must have experienced total cessation of menses for ≥ 1 year and be greater than 45 years in age, OR, in questionable cases, have a follicle stimulating hormone (FSH) value >40 mIU/mL and an estradiol value < 40 pg/mL (<140 pmol/L). Subjects using HRT must have experienced total cessation of menses for ≥ 1 year and be greater than 45 years of age OR have had documented evidence of menopause based on FSH and estradiol concentrations prior to initiation of HRT.

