6.3 Studies Obtained During the Trial

Physical examination: to identify any changes in the subject's mental and medical conditions since baseline assessment that would make him/her ineligible for the study. This will occur at C1D15, C2D1 and monthly thereafter (1 cycle = 28 days).

ECOG PS: Any changes since baseline assessment should be recorded in the eCRF. Subjects having deterioration of ECOG PS to ≥ 2 will be excluded from the study. This will occur at C1D15, C2D1 and monthly thereafter (1 cycle = 28 days).

Obtain blood sample for IL-6 and E-selectin measurement. This will occur monthly while patients are on study.

Tumor assessments will be performed every 8 weeks (+/- 1 week) from randomization until the start of another anticancer therapy. A partial or complete response warrants confirmation no sooner than 4 weeks and no later than 6 weeks after its initial observation.

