14.1.2 Secondary Endpoints

Secondary endpoints include progression-free survival (PFS), overall survival (OS), and toxicity. Toxicity will use the CTCAE 4.0 and will summarize the worst grade per toxicity, per patient.

Additional secondary endpoints relate to biological correlates, including E-Selection, IL-6, the pre-metastatic niche density, pSTAT3, and baseline HGF. Because the nature of these secondary endpoints is exploratory, we will not consider the issue of multiple comparisons and the according adjustment of p-values.

To determine an association between E-selectin, IL-6 and pre-metastatic niche density, we will conduct a pairwise correlation test (linear regression). When the sample size is 28, the linear regression test of rho=0 (alpha = 0.050 one-sided) for one normally distributed covariate will have 80% power to detect a correlation coefficient of 0.435.

To determine if the biological correlates (e.g, IL-6, E-selectin, pSTAT3, and HGF), are associated with progression-free survival (PFS), we will fit univariate or multivariate Cox proportional hazards model and report the corresponding p-values. The same method will be employed to evaluate the prognostic effect of pre-metastatic niches.

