14.2 Sample Size Accrual Rate

The previously noted sample size of 28 patients is anticipated to accrue over the course of 12 months.

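### The within-patient comparison is planned as PFS on pazopanib against TTP on the previous line, but the objective specifies TTP on both lines, and section 14.1.2 omits it

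*Combined protocol and SAP*

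**What the plan says.** The objective appears in the same words in the synopsis and as item 1.2.8: "To compare, within patient, time to tumor progression of 2nd-line therapy with time to tumor progression on pazopanib as 3rd-line therapy". That is the same endpoint on two lines of treatment in the same patient.

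The only sentence that turns this into an analysis is in the synopsis under Statistical Considerations: "we will also compare PFS on this study to time to progression on the previous line of therapy". It uses PFS on the pazopanib side and time to progression on the other.

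Section 14.1.2 opens with "Secondary endpoints include progression-free survival (PFS), overall survival (OS), and toxicity" and then gives methods for the biomarker correlations and the Cox models. It has no method for the within-patient comparison. Neither PFS nor TTP is defined anywhere in the document. No rule is given for deaths without progression, for censored pazopanib times or for dating progression on the earlier line, and no test is named.

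The two statements also name different comparators: the objective says second-line therapy and the synopsis analysis says the previous line. The inclusion criteria read "1 prior VEGF-TKI required" and "1 other prior systemic therapy allowed", so a second earlier therapy is optional.

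**The concern.** PFS and TTP conventionally differ in one respect: death without progression is an event for PFS and not for TTP. In this comparison the difference can matter on one side only. A patient who enrols has by definition survived the earlier line, so no prior-line time can have ended in death, whereas a pazopanib time can. An analyst who follows the synopsis sentence would set a quantity that death can shorten against one that death cannot shorten, and would report the result against an objective that asks for something else.

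What is at stake is the interpretation of one secondary objective: whether patients stay progression-free longer on pazopanib than they did on the line before. With no method in section 14.1.2, the choice of endpoint, the handling of deaths and the treatment of censored times could all be settled after the data are seen.

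**Working it through.** The plan gives no figure for this comparison, so there is nothing to reproduce. The check has a textual part and a sensitivity calculation.

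**Text side by side**

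| Place | Pazopanib side | Earlier side |
|---|---|---|
| Synopsis objectives; 1.2.8 | TTP | TTP on second-line therapy |
| Synopsis, Statistical Considerations | PFS | TTP on the previous line |
| 14.1.2 | not mentioned | not mentioned |

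The endpoint and the comparator line both differ between the objective and the analysis sentence.

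**Direction of this component.** Assume the conventional definitions (PFS event: progression or death; TTP event: progression only). Then PFS ≤ TTP in every patient, so using PFS on the pazopanib side can shorten that side or leave it unchanged, but never lengthen it. On the earlier side, wherever progression was observed, PFS and TTP are the same number because nobody died. Relabelling the earlier line as PFS would therefore change nothing.

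**Size.** Assume constant hazards: λp for progression and λd for death without progression. Let f = λd/(λp + λd), the share of PFS events that are deaths without progression.

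- Median TTP = ln 2/λp and median PFS = ln 2/(λp + λd), so the ratio is λp/(λp + λd) = 1 − f.
- If true TTP is the same on both lines and the two times are independent, P(pazopanib PFS > prior TTP) = λp/(λp + λp + λd) = (1 − f)/(2 − f). For f = 0.10 this is 0.90/1.90 = 0.474; for f = 0.20 it is 0.80/1.80 = 0.444.
- For paired times with a Gaussian-copula correlation of 0.5, the same probability was simulated (400,000 pairs per value of f).

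| f (assumed) | Median PFS / median TTP | P(pazopanib longer), independent | P(pazopanib longer), correlation 0.5 |
|---|---|---|---|
| 0 | 1.00 | 0.500 | 0.500 |
| 0.05 | 0.95 | 0.487 | 0.484 |
| 0.10 | 0.90 | 0.474 | 0.467 |
| 0.20 | 0.80 | 0.444 | 0.431 |
| 0.30 | 0.70 | 0.412 | 0.393 |

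With TTP on both lines, the probability would be 0.50 in every row. The documents do not give f, so the table shows a range and estimates nothing for this trial.

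**Scale against sampling error.** Section 14.2 sets the maximum: "The previously noted sample size of 28 patients is anticipated to accrue over the course of 12 months". The standard error of a proportion near one half in 28 pairs is √(0.25/28) = 0.094. At f = 0.10 the shift is 0.026 (independent) or 0.033 (correlated). At f = 0.20 it is 0.056 or 0.069. These are all below one standard error.

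**Other asymmetries.** On study, section 6.3 specifies "Tumor assessments will be performed every 8 weeks (+/- 1 week) from randomization until the start of another anticancer therapy". No schedule or criteria are given for dating progression on the earlier line, and the inclusion criteria do not state that the earlier line ended in progression. Because scanning stops at the next therapy, some pazopanib progression times can be censored. These features could move the comparison in either direction, and the documents give nothing from which to quantify them.

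**The case against.** The strongest reply is that this is loose synopsis wording beneath a clear objective. Item 1.2.8 still says TTP on both lines, and the endpoint list in 14.1.2 is introduced as inclusive, so it need not be complete. A reader might infer that the synopsis sentence is the operative plan because section 14 is silent; the documents do not settle that. What remains is that the only analysis sentence contradicts the objective and no other text resolves it.

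A second reply is that the effect may be negligible. Entry requires ECOG 0–1, and sections 6.3 and 6.4 continue scanning until another therapy starts, so deaths without progression may be few. If there are none, PFS and TTP coincide. Even at f = 0.20 the shift is within one standard error for 28 pairs. This stands as a limit on size. It does not make the analysis match the objective.

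A third reply is that TTP is not neutral either. The asymmetry comes from selecting patients who survived the earlier line, and a change of endpoint does not remove that selection. Censoring deaths on pazopanib treats those patients as having the same future progression risk as survivors. If they were close to progressing, that favours pazopanib. This also stands, and it is why a PFS-based sensitivity analysis belongs beside the TTP analysis.

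**Conclusion.** The point holds as a mismatch between objective and analysis: TTP on both lines in the objective, PFS against TTP in the only analysis sentence, and nothing in 14.1.2. Under conventional definitions, following the analysis sentence can only shorten the pazopanib side. With constant hazards the median shrinks by the fraction f, from no effect at f = 0 to a ratio of 0.90 at f = 0.10 and 0.80 at f = 0.20.

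A reader might infer that the comparison as a whole is biased against pazopanib, or that a true ratio of 1.0 would appear as 0.8–0.9. The documents support neither. They define neither endpoint, give no value for f, and leave prior-line progression to be dated retrospectively without a stated schedule, so the net direction is unknown. This is a secondary objective with no stated alpha, power or threshold, and it does not enter the response-count rule in 14.1.1. The plan should be corrected, but the primary conclusion does not depend on it.

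**What to change.** In the synopsis statistical section and in 14.1.2:

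- Define PFS and TTP, and use TTP on both lines for this comparison so that the analysis matches the objective.
- Restrict it to patients with a documented start date and progression date on the immediately preceding line, and report how many qualify. Reconcile the second-line wording of the objective with the previous-line wording of the analysis, since a patient with one earlier therapy has no second line to compare.
- Analyse the paired ratio (pazopanib TTP divided by prior TTP) with a method that keeps censored pazopanib times, such as a Kaplan-Meier estimate of the ratio. State its assumption that censoring is non-informative on the ratio scale. The censored and true ratios share the prior TTP as denominator, so the assumption generally fails unless the ratio is independent of prior TTP.
- Report the PFS-based ratio as a sensitivity analysis, because censoring deaths can favour pazopanib.

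The cost goes slightly beyond wording. Section 4.1.1.2 collects prior systemic treatments but does not name prior-line start or progression dates, so these must be recorded. Patients without them drop out of an analysis that has at most 28 pairs. Sample size and the primary decision rule do not change.
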